4.5.2 Adverse Events

All reported AEs will be classified by system organ class (SOC), preferred term and lower level term using Version 17.1 of MedDRA.

Summaries will be presented by SOC and preferred term.

A treatment emergent AE (TEAE) is defined as an AE with a start date on or after the first dose of IMP within this OLE study. If an AE has a partial start date and it is unclear from the partial date (or the stop date) whether the AE started prior to or post first dose of IMP then the AE will be considered treatment emergent. If the start date of the AE is the same as the date of first dose of IMP and the plausible relationship to study medication is marked on the CRF as "Prior to study medication" then the AE will not be considered treatment emergent.

An AE will be considered treatment-related if the plausibility relationship to study medication is recorded on the CRF as 'yes'. If the data on plausibility relationship to study medication is missing then the AE will be considered treatment-related.

An AE will be considered leading to permanent discontinuation of study medication if the action taken with study medication is recorded on the CRF as 'study medication stopped'.

An AE will be considered fatal if the outcome is recorded on the CRF as 'patient died'.

The following summaries will be generated:

- Overall summary of AEs, including number of patients reporting each of; TEAEs, treatment related TEAEs, TEAEs leading to withdrawal, treatment related TEAEs leading to withdrawal, serious TEAEs, treatment related serious TEAEs.
- Summary of TEAEs.
- Summary of treatment-related TEAEs.
- Summary of TEAEs by maximal severity.
- Summary of TEAEs by sex.
- Summary of serious TEAEs.
- Summary of treatment-related serious TEAEs.
- Summary of TEAEs leading to permanent discontinuation of study medication.

- Summary of treatment-related TEAEs leading to permanent discontinuation of study medication.
- Summary of fatal TEAEs.
- Summary of TEAEs by time of first onset of AE.
- Summary of TEAEs by time to AE resolution.
- List of patients experiencing TEAEs by SOC and preferred term.

For the summary of TEAEs by maximal severity, for each patient, the worst severity recorded by preferred term, SOC and overall will be used for summary purposes. If severity is missing, the worst case (severe) will be assumed.

For the summary of TEAEs by time of first onset of AE, data will be summarized under the following categories:

- Weeks 1 to 2 (Day 1 to 14).

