- Weeks 3 to 6 (Day 15 to 42).
- Weeks 7 to 10 (Day 43 to 70).
- Weeks 11 to 14 (Day 71 to 98).
- >14 weeks (> Day 98).

The time to first onset of AE will be calculated for TEAEs as:

$$\text{Start date of AE} - \text{Date of first dose of OLE IMP} + 1$$

If patients have multiple occurrences of an AE then the AE will be counted once for the first occurrence only. Percentages will be based on the number of patients in the safety analysis set who have a visit or follow-up call within each time period above.

For the summary of TEAEs by time to AE resolution, data will be summarized under the following categories:

- 1 week (≤ 7 days).
- 2 weeks (8 to 14 days).
- 3 weeks (15 to 21 days).
- 4 weeks (22 to 28 days).
- >4 weeks (>28 days).
- Ongoing (for AEs not resolved).

The time to AE resolution will be calculated for TEAEs as:

$$\text{Stop date of AE} - \text{Start date of AE} + 1$$

If patients have multiple occurrences of an AE then the AE will be counted once for the occurrence with the longest time to AE resolution. However, if any of the AEs are not resolved, then the AE will be counted once within the 'Ongoing' category.

For time of first onset of AE and time to AE resolution, partial or missing dates will be handled according to Section 4.1.2.2. If an AE has a partial start date and it is unclear from the partial date (or the stop date) whether the AE started prior to or post first dose of IMP then the start date will be imputed as the date of first dose of IMP in the OLE (Day 1). The start and stop day of the AE relative to the first dose of IMP (as recorded on the CRF) will be calculated as per Section 4.1.3. For partial dates, if it is clear from the partial date that

the start/stop day was prior to the first dose of IMP, then 'pre' will be listed, similarly if it is clear that the event was post the first dose of IMP then 'post' will be listed as the start/stop day as appropriate.

All AEs will be listed. Listings will include the start and stop day of the AE, a flag for treatment emergence, and limited demographic information about the patient (age, sex, race and weight at screening). A separate listing will be provided for pre-treatment AEs, serious AEs and events of special interest (see [Appendix 1](#)).

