Table Number	Title	Analysis Set
Table 9.17.2.4	Summary of Cognitive Assessment Battery Parent Measures - Behavior Report Form	Safety Analysis Set
Table 10.1	Summary of Exposure	Safety Analysis Set
Table 10.2	Summary of Exposure - Excluding Study GWEP1332 Part A	Safety Analysis Set
Table 10.3.1	Summary of Exposure - Patients Taking Clobazam	Safety Analysis Set
Table 10.3.2	Summary of Exposure - Patients Not Taking Clobazam	Safety Analysis Set
Table 10.4.1	Summary of Exposure - Core Study Actual Treatment of Placebo	Safety Analysis Set
Table 10.4.2	Summary of Exposure - Core Study Actual Treatment of Active	Safety Analysis Set
Table 10.5.1	Summary of Exposure - Core Study Actual Treatment of Placebo and Taking Clobazam	Safety Analysis Set
Table 10.5.2	Summary of Exposure - Core Study Actual Treatment of Placebo and Not Taking Clobazam	Safety Analysis Set
Table 10.5.3	Summary of Exposure - Core Study Actual Treatment of Active and Taking Clobazam	Safety Analysis Set
Table 10.5.4	Summary of Exposure - Core Study Actual Treatment of Active and Not Taking Clobazam	Safety Analysis Set
Table 10.6	Summary of Patient-years (On Treatment) by Modal Dose Group	Safety Analysis Set
Table 11.1	Overall Summary of Treatment Emergent Adverse Events	Safety Analysis Set
Table 11.2	Summary of Treatment Emergent Adverse Events	Safety Analysis Set
Table 11.3	Summary of Treatment-Related Treatment Emergent Adverse Events	Safety Analysis Set
Table 11.4	Summary of Treatment Emergent Adverse Events by Maximal Severity	Safety Analysis Set
Table 11.5	Summary of Treatment Emergent Adverse Events by Sex	Safety Analysis Set
Table 11.6	Summary of TEAEs by Time of First Onset of AE	Safety Analysis Set
Table 11.7	Summary of TEAEs by Time to AE Resolution	Safety Analysis Set
Table 11.8	List of Patients Experiencing Treatment Emergent Adverse Events by System Organ Class and Preferred term	Safety Analysis Set
Table 12.1	Summary of Serious Treatment Emergent Adverse Events	Safety Analysis Set
Table 12.2	Summary of Treatment-Related Serious Treatment Emergent Adverse Events	Safety Analysis Set
Table 12.3	Summary of Treatment Emergent Adverse Events Leading to Permanent Discontinuation of Study Medication	Safety Analysis Set
Table 12.4	Summary of Treatment-Related Treatment Emergent Adverse Events Leading to Permanent Discontinuation of Study Medication	Safety Analysis Set

Table Number	Title	Analysis Set
Table 12.5	Summary of Fatal Treatment Emergent Adverse Events	Safety Analysis Set

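### Table 11.6 counts first onsets only but keeps patients who have already had the AE in later denominators, which creates a spurious decline across its three 28-day windows

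*SAP*

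**What the plan says.** SAP section 4.5.2 (Adverse Events) defines the table listed in SAP Appendix 5 as Table 11.6, "Summary of TEAEs by Time of First Onset of AE". Onset is sorted into five windows: Days 1-14, 15-42, 43-70, 71-98, and everything after Day 98.

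The numerator rule is: "If patients have multiple occurrences of an AE then the AE will be counted once for the first occurrence only". The denominator rule is that percentages are "based on the number of patients in the safety analysis set who have a visit or follow-up call within each time period". Nothing in the section removes a patient from a later denominator once that patient has had the AE. AE summaries are presented by SOC and preferred term.

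No other AE table in Appendix 5 has a time-on-drug axis: Table 11.7 concerns time to resolution, and Tables 11.1-11.5 and 12.1-12.5 are not split by time. Patient-years are planned only for exposure by modal dose group (SAP 4.5.8.13, Table 10.6), so no exposure-adjusted AE rate is planned.

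**The concern.** A patient whose first nausea was on Day 10 cannot have a first nausea in Days 43-70, but is still counted among the patients in whom one could have been seen. The denominator is adjusted for who is still observed, not for who is still at risk of a first onset. The result is neither the risk among event-free patients nor a share of overall incidence, which would need a fixed N.

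The primary objective is long-term safety and tolerability, and this is the one planned AE table that shows when events start. Weeks 3-6, 7-10 and 11-14 are adjacent columns of equal length, so readers will compare them directly. A fall across them that comes only from the denominator could be read as patients growing tolerant of GWP42003-P.

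**Working it through.** **Inputs from the documents.** Windows and counting rules: SAP 4.5.2. Maximum duration 208 weeks: protocol 4.1. Planned contacts: Days 1, 15, 29 and 85, with a call 4 weeks after Visit 3, at about Day 57 (protocol 9.2.1-9.2.4). Each of the first four windows therefore contains a planned contact, and nearly every retained patient enters each denominator whatever their AE history. The plan states no figure to reproduce.

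**Assumptions.** The documents give no AE rates, so a constant 28-day onset risk r is varied from 1% to 30%. There is no loss to follow-up at first, and the last window is run to Day 728.

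**Formulas.** The proportion still free of the AE at day t is S(t) = (1 - r)^(t/28). For a window from a to b:

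- SAP percentage = S(a) - S(b), because patients with an earlier onset stay in the denominator.
- At-risk percentage = 1 - S(b)/S(a).

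**Worked case, r = 20%.** S(14) = 0.894, S(42) = 0.716, S(70) = 0.572, S(98) = 0.458, S(728) = 0.003. The SAP rule gives 0.894 - 0.716 = 17.9%, 0.716 - 0.572 = 14.3% and 0.572 - 0.458 = 11.4% (differences taken before rounding). The at-risk figure is 20.0% in all three windows.

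**Range under the SAP rule (%).**

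| Assumed 28-day risk | Days 1-14 | 15-42 | 43-70 | 71-98 | 99-728 | Ratio of 71-98 to 15-42 |
|---|---|---|---|---|---|---|
| 1% | 0.5 | 1.0 | 1.0 | 1.0 | 19.5 | 0.98 |
| 5% | 2.5 | 4.9 | 4.6 | 4.4 | 57.2 | 0.90 |
| 10% | 5.1 | 9.5 | 8.5 | 7.7 | 62.7 | 0.81 |
| 20% | 10.6 | 17.9 | 14.3 | 11.4 | 45.5 | 0.64 |
| 30% | 16.3 | 25.1 | 17.6 | 12.3 | 28.7 | 0.49 |

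The ratio in the last column is (1 - r)^2, since each 28-day window is the previous one times (1 - r).

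**Shape of the whole row.** The printed percentage rises from the first to the second window unless the 14-day risk exceeds 38.2% (28-day risk above 61.8%). It rises again into the last window unless the 28-day risk is about 50% or more. Rescaled to 28 days, the 20% row falls throughout: 21.1, 17.9, 14.3, 11.4, 2.0 (the last is 45.5 × 28/630).

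**Loss to follow-up.** A simulation with 2% loss per 28 days gives 17.7/14.2/11.3% for the three 28-day windows at r = 20%. With loss five times higher after an AE it gives 17.8/14.4/11.9%. At r = 5% the figures are 4.8/4.6/4.3% and 4.8/4.6/4.4%. The decline remains.

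**Candidate corrections under constant risk.** An at-risk denominator alone makes the three 28-day windows equal, but the last window then shows 68.5%, 90.7% and 99.3% at r = 5%, 10% and 20%. A rate per person-time at risk handles every window: person-time per patient is [S(a) - S(b)]/h with h = -ln(1 - r)/28, so onsets divided by person-time equal h throughout. At r = 20% that is -ln(0.8) = 0.223 per 28 patient-days in all five windows.

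**The case against.** The strongest reply is that the table is labelled as a summary by time of first onset and that the SAP never calls its percentages risks or rates. The share of patients seen in a window whose first onset fell there is a definable description. That is fair as to labelling. It does not stop readers comparing three equal adjacent columns, and 4.5.2 does not say what the percentage is meant to estimate.

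A reader might infer that the table makes AE risk appear to fall over the whole study. The documents do not support this. With windows of 14, 28, 28 and 28 days and then an open end, most rows would rise, fall across the middle three windows, and jump in the last one. For most rows the unequal and open-ended windows distort the table more than the denominator does.

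A reader might also quote the effect for an any-TEAE row, where high rates would make it very large. Section 4.5.2 specifies SOC and preferred-term presentation and names an overall level only for the maximal-severity summary, so such a row in Table 11.6 is an assumption.

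Finally, the reach is narrow. The other TEAE tables do not use these denominators, AE start days are listed, and there is no hypothesis testing.

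**Conclusion.** The point holds for the three 28-day windows. Table 11.6 pairs a first-onset numerator with a denominator that includes patients no longer at risk of a first onset, and a constant risk is then printed as a decline. The fall from Days 15-42 to Days 71-98 is 2% in relative terms at a 28-day risk of 1%, 10% at 5%, 19% at 10% and 36% at 20%. It is negligible for rare preferred terms and material for common terms and SOC rows.

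These sizes rest on assumed AE rates and a constant hazard; moderate dropout changes them little. The decline runs through all five windows only after rescaling to equal length. Overall TEAE incidence is not affected. The table should be corrected, but nothing in the study's main safety counts depends on it.

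**What to change.** In SAP 4.5.2, keep the first-onset count n. For each row (preferred term or SOC) and each window, add:

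- the number of patients still free of that term and under observation at the start of the window;
- the first-onset rate per person-time at risk, censored at first onset or end of observation.

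This makes the 14-day, 28-day and open-ended windows comparable. If percentages are kept, use the at-risk denominator and split the period after Week 14 into defined intervals. Changing the denominator alone would leave a last column close to 100% for common terms.

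The cost is a denominator that differs by row and slightly more programming for one table. AE start dates, contact dates and the first-dose date are already collected, so no new data are needed.

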9.1.12 Patient Diary

Seizure information (number and type of seizures) will continue to be collected through an IVRS telephone diary, completed weekly until the ‘End of Treatment’/Withdrawal visit. In addition, patients/caregivers will be instructed to complete the diary using IVRS at the following times:

- Once on the day before the ‘End of Taper Period’ visit.
- Once on the day before the Follow-up visit.

The patient or their caregiver will also continue to complete a paper diary daily to record daily usage of IMP, rescue medication, concomitant AEDs and AEs. Adequate training will be provided to the patient/caregiver in order to ensure data is being accurately collated via IVRS and paper diaries.

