9.2.3 Visit 3 (Day 29)

Visit 3 will take place 14 days after Visit 2 (28 days after Visit 1). A visit window of ± 3 days from the scheduled visit date is permitted, but it is preferred that the visit is performed on the scheduled visit day where possible.

The following assessments will be made at Visit 3: vital signs, physical examination (including height and body weight) and ECG. Clinical laboratory samples (blood and urine [where possible]) will be taken for hematology, biochemistry and urinalysis. The patient's IVRS report and paper diary will be reviewed and the information

recorded along with information regarding AEs, IMP, epilepsy-related hospitalizations, concomitant medications and/or changes to medication. The Investigator must assess adherence to the dosing regimen.

All IMP (used and unused) will be collected and a check of the returned IMP against usage should be made. Patients/caregivers will then receive an 8-week supply of IMP.

A safety telephone call must be made 4 weeks (± 7 days) after Visit 3. In addition, during titration of doses above 20 mg/kg/day, safety telephone calls must be made every 7 days (± 3 days) until stable dosing is achieved. During these calls, caregivers will be asked for information on AEs, epilepsy-related hospitalizations, concomitant medications and/or changes to medication.

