9.2.4 Visit 4 (Day 85)

Visit 4 will take place 8 weeks after Visit 3 (84 days after Visit 1). A visit window of ± 3 days from the scheduled visit date is permitted, but it is preferred that the visit is performed on the scheduled visit day where possible.

The following assessments will be made at Visit 4: vital signs, physical examination (including height and body weight) and ECG. Clinical laboratory samples (blood and urine [where possible]) will be taken for hematology, biochemistry and urinalysis. The patient's IVRS report and paper diary will be reviewed and the information recorded along with information regarding AEs, IMP, epilepsy-related hospitalizations, concomitant medications and/or changes to medication. The Investigator must assess adherence to the dosing regimen.

All IMP (used and unused) will be collected and a check of the returned IMP against usage should be made. Patients/caregivers will then receive a 12-week supply of IMP.

Following Visit 4, safety telephone calls must be made every 4 weeks (± 7 days). In addition, during titration of doses above 20 mg/kg/day, safety telephone calls must be made every 7 days (± 3 days) until stable dosing is achieved. During these calls, caregivers will be asked for information on AEs, epilepsy-related hospitalizations, concomitant medications and/or changes to medication.

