9.2.16 Safety Telephone Calls

From Visit 3 until the 'End of Treatment' visit, safety telephone calls must be made every 4 weeks (\pm 7 days). In addition, during titration of doses above 20 mg/kg/day, safety telephone calls must be made every 7 days (\pm 3 days) until stable dosing is

achieved. All safety telephone calls will assess AEs, epilepsy-related hospitalizations, concomitant medications and/or changes to medication.

A post-taper safety telephone call must also be made (see [Section 9.2.14](#)).

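### SAP 4.5.2 counts first AE onsets by start date but divides by patients with a contact dated in the window, so Weeks 7–10 percentages depend on how fully safety calls are recorded

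*SAP*

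**What the plan says.** SAP 4.5.2 defines five windows for time of first onset: Days 1–14, 15–42, 43–70, 71–98 and after Day 98. The third is "Weeks 7 to 10 (Day 43 to 70"). Time to onset is the AE start date minus the date of first OLE dose, plus 1. On repeat events the SAP says: "If patients have multiple occurrences of an AE then the AE will be counted once for the first occurrence only". The denominator is the "number of patients in the safety analysis set who have a visit or follow-up call within each time period above". Nothing limits the numerator to patients who are in that denominator, and *follow-up call* is not defined.

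The contacts around the third window are set in the protocol:

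- Section 9.2.3: "Visit 3 will take place 14 days after Visit 2 (28 days after Visit 1"), with a ±3-day window.
- Section 9.2.4: "Visit 4 will take place 8 weeks after Visit 3 (84 days after Visit 1"), with a ±3-day window.
- Section 9.2.3, between those visits: "A safety telephone call must be made 4 weeks (± 7 days) after Visit 3". Section 9.2.16 adds: "All safety telephone calls will assess AEs".

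AE capture does not depend on these contacts. Under protocol 9.1.12 the patient or caregiver is to "complete a paper diary daily to record daily usage of IMP, rescue medication, concomitant AEDs and AEs". The diary is reviewed at the next visit, and section 12.6 has AEs collected from Visit 1 through to the Follow-up visit.

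**The concern.** The numerator follows when an event began. The denominator follows when somebody was in contact with the patient. These agree only if every patient under observation has a recorded contact in every window. A patient whose safety call was missed or not recorded, and who reports at Visit 4 an event that began on Day 50, is counted above the line and not below it.

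Safety is the primary endpoint, and Table 11.6 is the only planned table showing when AEs start. Its use lies in comparing one window with the next. If coverage by recorded contacts is lower in one window than in its neighbours, the percentages differ for a reason unrelated to AE risk.

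**Working it through.** **Step 1. Place the scheduled contacts in the windows.** Day 1 is the date of Visit 1 (SAP 4.1.3). Visit days and tolerances are from protocol 9.2.2 to 9.2.4.

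| Contact | Derivation | Days | Onset window |
|---|---|---|---|
| Visit 1 | – | 1 | Weeks 1–2 |
| Visit 2 | 15 ± 3 | 12–18 | Weeks 1–2 or 3–6 |
| Visit 3 | 29 ± 3 | 26–32 | Weeks 3–6 |
| Safety call | (29 ± 3) + (28 ± 7) | 47–67 | Weeks 7–10 |
| Visit 4 | 85 ± 3 | 82–88 | Weeks 11–14 |

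The call limits are 29 − 3 + 28 − 7 = 47 and 29 + 3 + 28 + 7 = 67, so the call lies wholly inside Days 43–70. No scheduled clinic visit can fall there. Each of the first four windows contains a required AE contact, but Weeks 7–10 is the only one where that contact is a call alone.

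**Step 2. Write down the reported percentage.** Among patients under observation in a window, let f be the share with a first onset of a given AE, and c the share with a counted contact. With the numerator unrestricted:

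reported % = 100 × f / c, against 100 × f when all patients under observation are the base. The inflation factor is 1/c.

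The documents give neither f nor c; the values below are assumptions.

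| c | 1/c | f = 5% prints as | f = 10% prints as |
|---|---|---|---|
| 100% | 1.00 | 5.0% | 10.0% |
| 95% | 1.05 | 5.3% | 10.5% |
| 90% | 1.11 | 5.6% | 11.1% |
| 80% | 1.25 | 6.25% | 12.5% |

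**Step 3. Restrict the numerator instead.** Suppose the programmer counts only onsets in patients who are in the denominator. If onset is unrelated to contact, the percentage becomes (f × c)/c = f, which is unbiased. But a share 1 − c of the onsets in that window leaves the table: 5%, 10% or 20% of them at the three lower values of c. Neither programming choice is free of cost, and the SAP does not choose between them.

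**Step 4. Leave the safety calls out.** If *follow-up call* meant only the post-treatment contacts, c in Weeks 7–10 would be little more than the share of patients who had already stopped or attended unscheduled visits. The percentage exceeds 100% only when c < f. For example, an assumed c = 3% with f = 5% gives 100 × 0.05/0.03 = 167%.

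**The case against.** The strongest reply is that the rule says visit *or* call, and the protocol requires an AE safety call inside Days 43–70. If every call is made and recorded, every patient who remains under observation is in the denominator and nothing is inflated. Other contacts add coverage: weekly calls while doses above 20 mg/kg/day are being titrated (protocol 9.2.16), and extra clinic visits for dose adjustment (protocol 8.1.2). This stands. The absence of a clinic visit does not by itself make the denominator wrong.

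A reader might go further and infer that the Weeks 7–10 denominator consists almost entirely of patients who have left treatment, so that percentages near or above 100% should be expected. Some wording points that way. The protocol calls the 4-weekly contacts safety telephone calls and keeps *follow-up* for the post-dosing visit, which may be by telephone. SAP Table 2 names only a Post-Taper Safety Call and a Safety Follow-Up. But Table 2 is a list of visit labels and is not exhaustive: it omits protocol Visits 9 to 12. Neither of its two entries is titled a follow-up call. Leaving out a call that the protocol places squarely in the window is a strained reading, and the extreme percentages also need assumed counts that the documents do not supply.

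It is also true that the tables of overall incidence, severity, seriousness, discontinuation and fatal events do not use this denominator, that all AEs are listed with their start day, and that no hypothesis is tested. That limits the consequence. It does not repair the mismatch in Table 11.6.

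**Conclusion.** The point holds in a limited form. The denominator rule in SAP 4.5.2 can leave out patients whose events are in the numerator, and Weeks 7–10 is the most exposed of the first four windows because its scheduled contact is a call alone. On the natural reading, where the safety calls count, inflation is 1/(call completion): about 1.05 to 1.25 if 95% to 80% of patients under observation have a recorded contact. Those completion rates are assumptions, and the figure also assumes an unrestricted numerator. Much larger distortion, including values above 100%, would need the safety calls to be excluded. The documents leave that open only through an undefined term and do not indicate it as the intention. The effect is confined to one descriptive table.

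**What to change.** Replace the denominator sentence in SAP 4.5.2 with one stating that percentages for each window are based on safety-set patients still under AE follow-up at its start, that is, with a date of last contact on or after the first day of the window, whether or not any contact is dated inside it. Last contact should include any report from a caregiver and the date of death. An event that starts in a window must be reported on or after its start, so every numerator patient is then in the denominator and no percentage can exceed 100%. Patients who left earlier still drop out of later windows, as they should.

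Defining *follow-up call* to include the protocol safety calls would remove the ambiguity, but not the mismatch for a patient whose call was missed. The denominator above deals with both.

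The cost is one SAP sentence and a simple derivation from the last-contact date. No new data are needed.

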12.6 Reporting Procedures for All Adverse Events

All AEs (including SAEs) occurring during the study will be reported on the running logs in the AE section of the CRF. This includes all events from the time following enrollment (Visit 1) to post study follow-up (Follow-up visit), whether or not attributed to IMP and observed by the Investigator or patient.

For the patient's expected seizure types, these do not routinely require documentation as AEs. However, any worsening, including change in the pattern or severity of seizures must be documented as an AE. Any AE which meets SAE criteria should still be reported as a SAE.

The following information will need to be provided for all AEs:

A) Adverse Event (Diagnosis or Syndrome if Known, or Signs and Symptoms)

Where the Investigator cannot determine a diagnosis, signs or symptoms should be recorded on the AE section of the CRF. Once a diagnosis has been determined the AE section of CRF must be updated to reflect the diagnosis in replacement of the original symptoms. In circumstances, where only a provisional diagnosis is possible (working diagnosis), the CRF must be updated to reflect the provisional diagnosis in replacement of the original symptoms. In some circumstances it may be relevant for the Investigator to include the symptoms alongside the diagnosis in the verbatim event description. However, the diagnosis (full or provisional) should be clearly stated e.g., fever and malaise due to a respiratory tract infection.

B) Adverse Event Start Date and Stop Date

The start and stop dates of the event must be provided. All AEs require these fields to be completed in full. Partial dates or missing dates are not normally acceptable and significant effort must be undertaken to obtain any unknown information. If a precise date is not known an estimated date should be provided instead. When a complete date cannot be given then record as much information as possible (i.e., month and year or in exceptional circumstances just year). When the actual start date becomes known the CRF must be updated to replace the previously recorded date.

C) Outcome

The outcome of the event must be recorded accurately and classified into one of the following categories:

- Recovered.
- Recovered with sequelae.
- Continuing.

- Patient died.

D) Severity

When describing the severity of an AE the terms mild, moderate, or severe should be used. Clinical judgment should be used when determining which severity applies to any AE.

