13.1 Sample Size, Power and Significance Levels

As this is an open label safety study, there is no formal sample size calculation. All patients who wish to continue on IMP from the populations included in the double-blind Phase 2 and Phase 3 Core Studies in DS and LGS will be eligible for inclusion. Approximately 680 patients will be enrolled.

All data collected during this study will be summarized across time, using appropriate descriptive statistical methods. There will be no formal hypothesis testing.

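### SAP 4.5.2 bins AE resolution time by dates and ignores the CRF outcome, so a fatal AE with a stop date is tabulated as resolved

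*SAP*

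**What the plan says.** SAP 4.5.2 introduces the calculation with "The time to AE resolution will be calculated for TEAEs as" and then gives stop date minus start date plus one. The bins are up to 7 days, 8 to 14, 15 to 21, 22 to 28 and over 28 days. The only other row is "Ongoing (for AEs not resolved").

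Where a patient has several occurrences of the same AE, the one with the longest time to resolution is counted, subject to one override: "However, if any of the AEs are not resolved, then the AE will be counted once within the 'Ongoing' category". Partial or missing dates are referred to SAP 4.1.2.2, which imputes towards the longest duration and exempts only ongoing AEs from stop-date imputation.

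Protocol 12.6 B says of dates: "The start and stop dates of the event must be provided. All AEs require these fields to be completed in full". Protocol 12.6 C says of outcome: "The outcome of the event must be recorded accurately and classified into one of the following categories", and lists Recovered, Recovered with sequelae, Continuing and Patient died.

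The SAP does use that field elsewhere in the same section: "An AE will be considered fatal if the outcome is recorded on the CRF as" patient died. Fatal TEAEs have their own summary, Table 12.5. The resolution summary is Table 11.7.

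**The concern.** The CRF distinguishes four outcomes. Table 11.7 has rows that suit recovery and continuation, but none for death. The resolution rule takes dates as its input and nothing in it removes a fatal AE, so an event that ended because the patient died is handled in the same way as one from which the patient recovered.

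Table 11.7 is the only planned table on how long AEs last, and the AE profile is part of the primary endpoint. A reader of the table could not tell which entries in a duration bin are recoveries and which are deaths. For a preferred term whose only occurrences were fatal and carried stop dates, every patient with that term would appear as resolved. SAP 1.2.1 itself describes Dravet syndrome as having high mortality, so fatal AEs are foreseeable.

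**Working it through.** The plan gives no figure to reproduce, so the check is to trace the rule as written.

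**Inputs.** Formula, bins and multiple-occurrence rule: SAP 4.5.2. Outcome categories and the stop-date requirement: Protocol 12.6. Imputation: SAP 4.1.2.2. Assumption: the stop date of a fatal AE is the date of death. Neither document says how it is set.

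**Step 1: one fatal AE.** Duration = stop − start + 1. The intervals are illustrative.

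| Days from onset to death | Duration (days) | Row in Table 11.7 |
|---|---|---|
| 0 | 0 + 1 = 1 | 1 week |
| 3 | 3 + 1 = 4 | 1 week |
| 6 | 6 + 1 = 7 | 1 week |
| 7 | 7 + 1 = 8 | 2 weeks |
| 30 | 30 + 1 = 31 | >4 weeks |

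Every case lands in a time-to-resolution bin. The shortest bin applies only when death comes within 6 days of onset.

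**Step 2: outcomes against rows.**

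| CRF outcome | Row reached under SAP 4.5.2 |
|---|---|
| Recovered | Duration bin |
| Recovered with sequelae | Duration bin |
| Continuing | Ongoing |
| Patient died, stop date present | Duration bin |
| Patient died, stop date absent | Not settled: SAP 4.1.2.2 imputes unless the AE counts as ongoing |

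The fourth line is the wrong entry. The fifth is unspecified, and either result misdescribes the event.

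**Step 3: several occurrences.** Suppose a patient has an earlier episode, recovered, with stop − start = 19 days, and later a fatal occurrence of the same term with stop − start = 2 days. The durations are 19 + 1 = 20 and 2 + 1 = 3. The longest is counted, so the patient appears once, under 3 weeks, on the strength of the non-fatal episode. An unresolved occurrence would override this; a fatal one does not.

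**Step 4: frequency.** The number of fatal AEs, the share with a stop date and the onset-to-death interval are not in the documents. The share of fatal AEs falling in the shortest bin could be anything from 0% to 100%.

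**The case against.** The best counter-argument is that the SAP does not define resolution by the stop date. The date formula gives the length. Separately, AEs that are not resolved go to Ongoing, and since that term is undefined, a programmer could place a fatal AE there. The date requirement in Protocol 12.6 B also cannot be wholly literal, because a continuing AE has no stop date, so it does not prove that every fatal AE carries one. Both points stand as limits: the wrong entry arises for fatal AEs that have a stop date, under the literal reading. They do not clear the rule. The formula is applied to TEAEs without exception, no text diverts a death, and the alternative of calling a death ongoing is also wrong.

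The second argument is that little turns on it. Table 12.5 shows fatal TEAEs, Table 12.1 and Listing 12 show serious ones, and the AE listings carry start and stop days. The resolution table is not among the AE summaries in Protocol 13.6.2.1; it is a SAP addition in a study with no hypothesis testing. This is right, and it is why the point is minor. It does not make the entries in Table 11.7 correct.

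A reader might also infer more than the documents support:

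- **That deaths would mostly appear as resolution within a week.** No onset-to-death interval is given. Protocol 12.1.1 asks for the underlying cause of death as the term, so onset may long precede death.
- **That a blank stop date puts a fatal AE in Ongoing automatically.** SAP 4.1.2.2 points to imputation unless the AE is ongoing.
- **That other AEs still open at death are misplaced in the same way.** Recorded as Continuing, they already go to Ongoing and their stop dates are not imputed.

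**Conclusion.** Wrong as written, minor. A literal application of SAP 4.5.2 counts a fatal AE with a stop date as resolved in Table 11.7, and the longest-occurrence rule can replace a fatal occurrence with a longer non-fatal one. The conclusion rests on two conditions: that fatal AEs are given stop dates, as Protocol 12.6 B asks without exempting them, and that no unwritten programming convention diverts them.

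The number affected cannot be estimated. The mortality remark in SAP 1.2.1 gives no rate and concerns Dravet syndrome only, so it cannot be turned into a count for a study that also enrols LGS patients. The effect is limited to one descriptive table, matters chiefly for terms with fatal occurrences, and conceals no death, since Table 12.5 reports them.

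**What to change.** In SAP 4.5.2 and Table 11.7, assign rows from the CRF outcome:

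- Use the duration bins only when the outcome is Recovered or Recovered with sequelae, with the existing formula.
- Use Ongoing when the outcome is Continuing.
- Add a Fatal row for the outcome Patient died. It takes precedence over all other occurrences of the same term in that patient, including ongoing ones.
- State in SAP 4.1.2.2 or 4.5.2 that a stop date is not imputed in order to place a fatal AE in a resolution bin.

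AEs recorded as Continuing when a patient dies of another cause need no category of their own.

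The cost is a short addition to the SAP text, one extra row in Table 11.7 and a small programming change. The outcome field is already collected and already used in SAP 4.5.2 to identify fatal AEs.
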